9.11 Reports to the Ethics Committee and Regulatory Authorities

Upon completion of the study, the Investigator will provide the IRB with a summary of its outcome.

The relevant regulatory authorities will be provided with a Declaration of the End of a Clinical Trial form and safety report (or local equivalent) within 90 days of completion or within 15 days of a premature termination. These will also be provided to the IRB.

9.12 Confidentiality

All unpublished information that the Sponsor gives to the Investigator shall be kept confidential and shall not be published or disclosed to a third party without the prior written consent of the Sponsor.

When the Sponsor generates reports for presentations to regulatory agencies, one or more of the Investigators who has/have contributed significantly to the study will be asked to endorse the final report. The endorsement is required by some regulatory agencies.

The Investigator shall not make a patent application based on the results of this study and shall not assist any third party in making such an application without the written authorization of the Sponsor unless otherwise specified in the Clinical Study Agreement.

The subject must be informed that his/her personal study related data will be used by the Sponsor in accordance with the local data protection law. The level of disclosure must also be explained to the subject.

9.13 Records Retention

The Investigator must maintain all study documentation as confidential, and take measures to prevent accidental or premature destruction of these documents.

The Investigator must retain the study documents until at least 2 years after the last approval of a marketing application/new drug application for the indication investigated or at least 2 years have elapsed since the formal discontinuation of clinical development of the investigational product (eg the Investigational New Drug application is withdrawn). These documents should be retained for a longer period, however, if required by the applicable regulatory requirements or by an agreement with the Sponsor.

The Investigator must notify the Sponsor prior to destroying any study essential documents.

If the Investigator can no longer ensure archiving, he/she shall inform the Sponsor. The relevant records shall be transferred to a mutually agreed upon designee.

9.14 Publications

The Sponsor holds all publication rights to the data obtained from this study. Before any data from this study are published on the initiative of the Investigator, the Investigator should obtain written approval from the Sponsor. A manuscript will be sent to the Sponsor for review and written approval at least 60 days prior to submission to the publisher, and according to any additional publication details in the Investigator Agreement.

9.15 Subject Injury

In general, if a subject is injured as a direct result of the study drug, the Sponsor will pay for reasonable and necessary medical treatment for the injury, to the extent the expenses are not covered by the subject's medical insurance, a government program, or other responsible third party. If laws or regulations of the

locality in which the trial is taking place require additional payment of expenses, the Sponsor shall comply with such law or regulation. Where applicable, the Sponsor has taken specific national insurance.

11. APPENDICES

Appendix A - Clinical Laboratory Evaluations

Serum Chemistry: Aspartate aminotransferase (AST) Alanine aminotransferase (ALT) Alkaline phosphatase Gamma glutamyl transferase (GGT) Lactate dehydrogenase (LDH) Sodium Potassium Chloride Calcium Bicarbonate Inorganic phosphate Glucose Urea Uric acid (sUA) ^h Total bilirubin Direct bilirubin Creatinine Blood urea nitrogen (BUN) Total protein Albumin Creatinine phosphokinase (CPK) Glycosylated hemoglobin (HbA1c) ^a	Complete Blood Count^c White blood cell count (WBC) Red blood cell count (RBC) Hemoglobin Hematocrit (PCV) Mean cell volume (MCV) Mean cell hemoglobin (MCH) MCH concentration (MCHC) Platelet count Differential WBC
	Urinalysis^c: Microscopic examination Specific gravity pH Protein Glucose Ketones Blood Urobilinogen
	For Females Only: Urine pregnancy test ^d
	For Postmenopausal Females Only: Follicle-stimulating hormone (FSH) ^e
Lipid Panel^b: Total cholesterol High-density lipoprotein cholesterol (HDL-C) non-HDL-C	Serology^f: Hepatitis B surface antigen (HBsAg) Hepatitis C antibody Human immunodeficiency virus (HIV) ^g
	Urinary Biomarkers: Urinary albumin-to-creatinine ratio (UACR) ^h Kidney injury molecule 1 (KIM-1) ⁱ Liver fatty acid binding protein (L-FABP) ⁱ 8 hydroxy 2' deoxyguanosine (8-OHdG) ⁱ N-acetyl-β-D-glucosaminidase (NAG) ⁱ
Thyroid Testing^b: Triiodothyronine (T3) Thyroxine (T4) Free triiodothyronine (FT3) Free thyroxine (FT4) Thyrotropin/Thyroid stimulating hormone (TSH)	Blood Biomarkers: Soluble tumor necrosis factor receptor 1 (sTNFR1) ⁱ high sensitivity C reactive protein; (hs-CRP) ⁱ Estimated glomerular filtration rate (eGFR)

^aAt Visits 1, 3, and 6 only

^bAt Visits 2, 3, 4, 5, 6, and 7 only

^cAt Visits 1, 3, 4, 5, 6, and 7 only

^dFemales of childbearing potential only, at Visits 1, 3, 6 (Early Termination Visit only), and 7. Positive pregnancy result will result in hormone panel analyzed in serum

^ePostmenopausal females at Visit 1 only

^fOnly analyzed at Visit 2

^gHIV1/2 antibody test

^hResults at Visits 3, 4, 5, 6, and 7 will not be reported to Investigators, subjects, and the Sponsor staff. Investigators must not measure UACR or sUA at local sites

ⁱAt Visits 3, 4, 5, 6, and 7 only. These values are corrected with urinary creatinine.

Appendix B – Permitted and Prohibited Concomitant Medication

Permitted Medications/Must be Used	Class of Compound	Study Timepoint
≥1 glucose-lowering medication	Glucose-lowering agent	At least 12 months prior to Visit 1. It is preferable that these medications should not be changed from Visit 2 until the end of the study, however, if this is deemed clinically necessary, this is permitted and the subject does not need to be withdrawn from the study.
ACEI or ARB (not both) at least the minimal recommended dose	Angiotensin II inhibitors	At least 3 months prior to Visit 1, without any adjustments to this therapy for at least 4 weeks prior to the Visit 1, and continue with this treatment for the duration of the study.
Permitted Medications/Can be Used	Class of Compound	Study Timepoint
oral, injected, or implanted contraceptives and hormone-replacement therapy are permitted during the study	Contraceptives	Any time during the study.
Antihypertensive, antilipemic, antituberculous (pyrazinamide and ethambutol), diuretics (non-thiazide diuretics, thiazide diuretics, and loop diuretics)	Antihypertensive, lipid altering, or anti-tuberculosis agents	It is preferable that these medications should not be changed from Visit 2 until the end of the study, however, if this is deemed clinically necessary, this is permitted and the subject does not need to be withdrawn from the study.
diet remedies and exercise regimes	NA	Should not begin or stop from Visit 2 until the end of the study.
Permitted but caution to be applied and avoid maximum doses, if possible, if these agents are used	Class of Compound	Study Timepoint
[REDACTED]	[REDACTED]	Any time during the study.
[REDACTED]	[REDACTED]	Any time during the study.
[REDACTED]	[REDACTED]	Any time during the study.

--	--	--

Abbreviations: ACEI = angiotensin converting enzyme inhibitor; ARB = angiotensin II receptor blocker; BCRP = breast cancer resistance protein; CYP = cytochrome P450; NA = not applicable.

Prohibited Medications	Class of Compound	Study Timepoint
		Any time after Visit 2 until the end of the study.
		At any time prior to Visit 1 and for the duration of the study.
		Any time after Visit 2 until the end of the study.

[REDACTED]		
uricosuric agents	Uric acid-lowering therapy	Within 2 weeks of Visit 1 and for duration of the study.
[REDACTED]	[REDACTED]	Any time after Visit 2 until the end of the study.
XO inhibitors	Uric acid-lowering therapy	Within 2 weeks of Visit 1 and for duration of the study.
Other investigational drugs within previous 30 days prior to Visit 1 and for the duration of the study.		

Abbreviations: [REDACTED], NA = not applicable; [REDACTED]; [REDACTED]; [REDACTED]; XO = xanthine oxidase.

██████████ Statistical Programmer	Lead Programmer	0.1	██████████

Version History

Version #	Description of Changes	Version Date
Final Version 1.0	Not applicable	May 21, 2018
Amendment 1 Final Version 1.0	
 1. Section 7.6.3: Added a sensitivity analysis for primary efficacy endpoint. 2. Section 7.6.4: Added a new section to include subgroup analyses for the primary efficacy endpoint. 3. Section 7.6.5.1 Re-arranged and added scatter plots. 4. Section 7.8: 
 1) Added reference for population pharmacokinetic analysis. 2) Added analyses for pharmacokinetic plasma concentration of TMX-049. 5. Minor edits were made to other sections of the SAP, as needed, for consistency with the changes described above. 	April 12, 2019

Glossary of Abbreviations

Abbreviation	Term
AE	adverse event
ANCOVA	analysis of covariance
ATC	Anatomical Therapeutic Chemical
BLQ	below the limit of quantification
BMI	body mass index
BP	blood pressure
CKD-EPI	chronic kidney disease epidemiology collaboration equation
CL	confidence limit
CRF	case report form
CV	coefficient of variation
DB	double-blind
DBL	database lock
ECG	electrocardiogram
ET	early termination
HR	heart rate
ITT	intention-to-treat
LOCF	last observation carried forward
LLOQ	lower limit of quantification
MAR	missing at random
MedDRA	Medical Dictionary for Regulatory Activities
mITT	modified intent-to-treat
MMRM	mixed-effects model for repeated measures
NC	not calculated
NR	no result
OC	observed cases
PK	pharmacokinetic
PP population	per-protocol population
PT	preferred term
QTcB	Bazett corrected QT interval
QTcF	Fridericia corrected QT interval
REML	restricted maximum likelihood
SAE	serious adverse event
SD	standard deviation
SOC	system organ class
sUA	serum uric acid
TFLs	tables, figures, and listings
UACR	urinary albumin-to-creatinine ratio
WHO	World Health Organization

1. Source Documents

The Statistical Analysis Plan (SAP) was written based on the following documentation:

Document	Date	Version
Protocol	07 FEB 2018	Final version 2.0
eCRF	20 MARCH 2018	Draft version 01.014

2. Protocol Details

2.1 Study Objectives

The primary objective of this study is to assess the effect of 2 dose levels of TMX-049 on urinary albumin excretion in subjects with Type 2 diabetes and albuminuria (a urinary albumin-to-creatinine ratio [UACR] 200 to 3000 mg/g and an estimated glomerular filtration rate (eGFR) ≥ 30 ml/min/1.73m²). Effects of each TMX-049 dose on UACR will be assessed in terms of ratios using log-transformed UACR at Baseline and after a 12-week period of treatment.

The secondary objectives of this study are to assess the followings:

- The effect of each dose of TMX-049 on eGFR during the 12-week period of treatment
- The percentage of subjects with >30% decrease in UACR with Placebo and each dose of TMX-049 after 12 weeks of treatment
- The effect of each dose of TMX-049 on exploratory renal biomarkers during the 12-week period of treatment
- The effect of each dose of TMX-049 on serum uric acid (sUA) during the 12-week period of treatment
- The pharmacokinetics (PK) of TMX-049 in subjects with Type 2 diabetes and albuminuria
- Safety and tolerability of TMX-049

2.2 Overall Study Design

This is a randomized, placebo-controlled, double-blind, multicenter, Phase 2 study in subjects with Type 2 diabetes, UACR 200 to 3000 mg/g, and eGFR ≥ 30 ml/min/1.73m².

Potentially eligible subjects will attend an initial Screening Visit (Visit 1) and sign an informed consent document. After the subject's medical history is reviewed and inclusion/exclusion criteria for the trial assessed, urine and blood samples will be obtained and sent to a [REDACTED] central laboratory.

Subjects who have a UACR 200 to 3000 mg/g and eGFR ≥ 30 ml/min/1.73m² and meet all other protocol-specified eligibility criteria at Visit 1 will return for Visit 2. At Visit 2, subjects will have a physical examination including triplicate blood pressure

measurements, a standard 12-lead electrocardiogram (ECG), provide blood samples for repeat eGFR, and submit 2 consecutive day mid-stream first-morning void urine samples for Baseline UACR determination for confirmation of eligibility. Subjects will be given study medication to be used during a single-blind, placebo run-in phase and instructed to return their study medication to the site at Visit 3. All pre-randomization study visits will be completed in ≤ 6 weeks. Study medication will be self-administered by the subject qd. Study medication should be taken in the morning at about the same time each day, and taken with food (breakfast or a snack) rather than on an empty stomach beginning on the day after Visit 2.

Subjects who meet all eligibility criteria, including UACR 200 to 3000 mg/g and eGFR ≥ 30 ml/min/1.73m² at both Visit 1 and Visit 2 and who also have $\geq 80\%$ study medication compliance during the 2-week placebo run-in phase, will be randomized at Visit 3 in a 1:1:1 ratio to 1 of 3 treatment groups: Placebo, 40 mg of TMX-049, or 200 mg of TMX-049. Approximately 132 subjects will be randomized, with the expectation that 40 subjects per treatment group will complete 12 weeks of treatment and be included in the primary endpoint assessment. Randomization will be stratified by sUA (< 6.0 versus ≥ 6.0 mg/dL) and UACR (200 to < 300 mg/g versus 300 to ≤ 3000 mg/g) levels obtained at Visit 2. Study medication will be self-administered by the subject qd in the morning at about the same time each day and taken with food (breakfast or a snack), rather than on an empty stomach during the randomized treatment phase beginning on the day after Visit 3 and continued until the morning prior to Visit 6. The time of dosing and time of any food intake will remain consistent during the period of randomized treatment.

Randomized study subjects will return to the site after 2 (Visit 4), 6 (Visit 5), and 12 weeks (Visit 6) of double-blind treatment. Study medication compliance will be assessed by pill count at each visit. First-morning void urine samples will be collected on 2 consecutive days prior to each visit. Urine and blood samples for determination of eGFR, sUA levels, and other laboratory tests will be obtained prior to and after initiation of randomized treatment. Results of sUA and UACR will not be reported to Investigators, subjects, and the Sponsor staff during the randomized treatment phase of the study. The time of PK sample acquisition, the time of dosing prior to the PK sample acquisition, and whether the subject took study medication with or without food will be recorded in the appropriate sections of the case report form (CRF) based on verbal communications with the subjects.

[figure not shown]
At Visit 4, a sample will be obtained prior to TMX-049 dosing (trough sample). At Visit 5, a sample will be obtained 3 ± 1 hours after study medication dosing (t_{\max} sample). The timing of dosing can be adjusted to the time of visiting. At Visit 6, a sample will be obtained ≥ 6 hours (the ideal target is ≥ 8 hours) after study medication dosing (elimination phase sample). If a subject cannot visit within the

time window, a sample will be obtained when the subject visits, even out of the time window. If the trough sample is not obtained at Visit 4, the trough sample should be obtained at Visit 6, instead of the elimination phase sample. If the trough sample is obtained at Visit 4 and t_{max} sample is not obtained at Visit 5, the t_{max} sample should be obtained at Visit 6, instead of the elimination phase sample. Sites have the option to have a study participant return to the site on a separate day to obtain a properly timed Visit 4, 5, or 6 sample for PK analysis.

Safety assessment will be based on clinical laboratory evaluations, vital signs, physical examinations, and 12-lead ECG, which will be obtained prior to and during the period of randomized treatment.

All study subjects will attend an end of study follow-up Visit (Visit 7) 4 weeks after the last dose of study medication. Two consecutive day urine samples for UACR determination will be submitted by all subjects at this final visit. Urine and blood samples for determination of eGFR, sUA levels, and other laboratory safety tests will be obtained at Visit 7 or at Visit 6 (or the Early Termination [ET] Visit).

The study schema is illustrated below:

2.3 Sample Size and Power

Approximately 132 subjects will be randomized at a 1:1:1 ratio to each of the 3 treatment groups (40 mg TMX-049, 200 mg TMX-049, and Placebo). Assuming that 10% of all randomized subjects will not be included in the primary endpoint analysis, this would result in approximately 40 subjects per treatment group for inclusion in the primary endpoint assessment.

A sample size of 40 per group will have more than 80% power on the primary endpoint assessment to detect a difference in means of 35% reduction (-0.431 for

log-transformed value) of UACR assuming that the common standard deviation (SD) is 0.670 (log-scale) using a 2-group t-test with a 0.050 two-sided significance level.

3. Efficacy and Safety Variables

3.1 Primary Efficacy Endpoint(s)

The primary efficacy endpoint is the change from Baseline to Study Week 12 (Study Visit 6) in log-transformed UACR.

3.2 Secondary Efficacy Endpoints

The secondary efficacy endpoints include:

- Proportion of subjects with >30% reduction from Baseline to Study Week 12 (Study Visit 6) in UACR
- Change in eGFR (Baseline compared to Study Weeks 2, 6, 12/ET, and Follow-up visit)
- Change in UACR (Baseline compared to Study Weeks 2, 6, 12/ET, and Follow-up visit)
- Change in renal biomarkers (Baseline compared to Study Weeks 2, 6, 12/ET, and Follow-up visit)
- Change in sUA (Baseline compared to Study Weeks 2, 6, 23/ET, and Follow-up visit)

3.3 Safety Variables

The safety endpoints include:

- Proportion of subjects with reported adverse events (AEs), discontinuation due to AEs and serious adverse events (SAEs)
- Proportion of subjects with AEs considered by the Investigator to be related to study drug
- Proportion of subjects with mild, moderate, or severe AEs as assessed by the Investigator
- Changes from Baseline in vital signs, ECGs, and laboratory parameters

4. Pharmacokinetic/Pharmacodynamic variables

The Pharmacokinetic endpoint is the plasma concentrations of TMX-049 at Study Weeks 2, 6, and 12/ET.

5. Analysis populations

Unless otherwise specified, all efficacy analyses will be performed using the modified Intention-to-Treat (mITT) population, all sensitivity analyses will be

performed using the Per Protocol (PP) population and safety analyses will use Safety population. Pharmacokinetic (PK) analyses will be performed using the PK population.

5.1 All Subjects Population

All subjects who enrolled in the study, ie, signed informed consent, and had study assessments recorded in the database per the protocol will be included in the All Subjects population.

5.2 Randomized Population

All randomly assigned subjects will be included in the Randomized population. Randomized subjects are analyzed according to their randomized treatment.

5.3 Safety Population

All randomized subjects who received at least 1 dose of study drug will be included in the Safety population. Safety subjects are analyzed according to their actual treatment received.

5.4 Modified Intent-to-treat Population

The mITT population will consist of all randomized subjects who have at least 1 post randomization UACR assessment. Subjects in the mITT population will be analyzed according to their randomized treatment.

5.5 Per-Protocol Population

The PP population will consist of all subjects in the mITT population who do not experience any important protocol deviations leading to exclusion from the PP population. Subjects in the PP population will be analyzed according to their randomized treatment.

Protocol deviations are defined as any change, divergence, or departure from the study design or procedures defined in the study protocol. Important protocol deviations are a subset of protocol deviations and may significantly impact the correctness, accuracy, and/or reliability of the study data or that may significantly affect a subject's rights, safety, or well-being. **Section 5.5.1** details the deviations.

All protocol deviations that occur during the study will be considered prior to database lock (DBL) for their severity and impact.

5.5.1 Important Protocol Deviations Leading to Exclusion from the Per-Protocol Population

Type	Deviation	Method of Identification
Prohibited Medications	Subjects who have taken medications that are not permitted during the double-blind treatment period. A list of permitted and prohibited concomitant medication is provided in Appendix B in the protocol.	Manual review of blinded concomitant medications listing. [REDACTED] will provide the medical monitor with the list of concomitant medications taken by subjects. The medical monitor will review this list and note any prohibited medications. Subjects will be excluded if they were taking prohibited medications during the double-blind treatment period.
Noncompliance during 12-week double-blind treatment period	Subjects who had low study drug compliance (eg, repeated occurrence of compliance <80% during the double-blind treatment period)	Programmatic check based on the exposure and drug accountability data. Manual review will be performed for identifying subjects with low compliance rate during the double-blind treatment period.
Errors in Treatment Allocation	Subjects that received a wrong treatment at 1 or more study visits due to packaging or dispensing errors	Programmatic check based on unblinded IVRS database after the study is unblinded. The check will be done by comparing the bottle number that IVRS had assigned to the subject/visit against the bottle number actually used.
Clinical Trial Management System	[REDACTED] Clinical will provide the list of protocol deviations based on the clinical monitoring.	Manual review: The Sponsor will review this list and finalize any important protocol deviations which will then be included in the programming.

As defined in the table, the majority of the protocol deviations will be determined programmatically from the data. Those criteria which require clinical or medical monitoring interpretation will be reviewed prior to DBL, following discussion with the medical monitor and Teijin.

All the important protocol deviations leading to exclusion from the PP population occurring during the study will be reviewed and approved by Teijin prior to DBL and unblinding. Should other categories of important protocol deviations, not anticipated at the time of preparing this SAP, be identified during the study (and prior to unblinding), they will be documented in a separate document and included in all relevant protocol deviation reviews and approvals.

5.6 Pharmacokinetic Population

The PK population will consist of all subjects who received at least 1 dose of TMX-049 and had evaluable PK data. Subjects in the PK population will be analyzed according to their actual treatment received.

6. DATA Handling

6.1 Time points and Visit Windows

Day 0 is defined as the Baseline/Randomization visit (Study Visit 3). Day 1 is the first day of treatment. Relative days after Day 1 are calculated as (assessment date – Day 1 date) + 1. Relative days prior to Day 1 are calculated as (assessment date – Day 1 date).

The visit windows defined in the following table will be used for the by-visit analyses of the primary, the secondary and other endpoints. All other analyses will use the nominal study visit as defined in the study schedule and eCRF.

If there are multiple visits (scheduled or unscheduled) within a visit window, the measurement closest to the target day of the visit will be used in the analysis. If the measurements are equally distant to the target day, then the later one will be used in the analysis.

Time Point (Target Study Day)	Study Day Range for UACR*	Study Day Range for Serum Chemistry, Hematology, Lipid Panel, Urinalysis, Blood and Urine Samples for Biomarkers, Vital Signs	Study Day Range for ECG, Physical Examination	Study Day Range for HbA1C
Baseline	≤ 1	≤ 1	< 1	≤ 1
Week 2 (Day 14)	2 – 21	2 - 21		
Week 6 (Day 42)	22 – 63	22 - 63		
Week 12/ET (Day 84)	64 – 104	64 – 104	≥ 1	> 1
Week 12/ET + 28 Days (Day 112)	≥ 105	≥ 105		

*: This is for the first morning void UACR sample collection.

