7.5.4.4 Visit 5: Study Day 42 ± 7 Days

The following information and procedures will be recorded and performed at Visit 5:

- pre-Visit 5 call for reminder of urine collection and dosing approximately 3 hours before the visit before visit
- contact IXRS

- study drug administration; see [Section 7.4.1](#)
- urine sample for UACR (2 consecutive day mid-stream, first-morning void urine samples to be collected at the subject's home on the morning before and the morning of Visit 5)
- complete blood count
- serum chemistry profile (including sUA and serum creatinine to calculate eGFR); see [Appendix A](#) for the evaluations to be performed
- thyroid hormones
- lipid panel
- urinalysis
- blood (plasma and serum) and urine sample for biomarkers (the mid-stream, first-morning void urine samples collected by the subjects at home will be used for the analysis of biomarkers)
- treatment-emergent adverse event recording
- concomitant medication review
- vital signs, consisting of supine blood pressure, supine pulse rate, and oral body temperature
- body weight
- PK sampling, see [Section 7.7.1](#)
- 3 study drug treatment kits will be dispensed to the subject
- dispense urine collection supplies (for collection of 2 consecutive day first-morning void urine samples on the morning before and the morning of the subsequent visit)
- assess double-blind compliance

7.5.4.5 *End of Treatment Visit 6: Study Day 84 ± 7 Days or Early Termination Visit*

The following information and procedures will be recorded and performed at Visit 6:

- contact IXRS
- pre-Visit 6 call for reminder of urine collection, dosing in the morning before the visit
- dispense urine collection supplies (for collection of 2 consecutive day first morning void urine samples on the morning before and the morning of the subsequent visit)
- urine sample for UACR (2 consecutive day mid-stream, first-morning void urine samples to be collected at the subject's home on the morning before and the morning of Visit 6)
- complete blood count
- serum chemistry profile (including sUA and serum creatinine to calculate eGFR); see [Appendix A](#)

for the evaluations to be performed

- thyroid hormones
- lipid panel
- HbA1c
- urinalysis
- urine pregnancy test for female subjects of childbearing potential (only Early Termination Visit)

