- blood (plasma and serum) and urine sample for biomarkers (the mid-stream, first-morning void urine samples collected by the subjects at home will be used for the analysis of biomarkers)
- treatment-emergent adverse event recording
- concomitant medication review
- vital signs, consisting of supine blood pressure, supine pulse rate, and oral body temperature
- body weight
- resting 12-lead ECG
- physical examination
- PK sampling; see [Section 7.7.1](#)
- assess double-blind compliance

7.5.4.6 *End of Study Follow-up (Visit 7): Visit 6/ET+28 ± 7 days*

The following information and procedures will be recorded and performed for all subjects as part of the follow-up assessments:

- contact IXRS
- pre-Visit 7 call for reminder of urine collection
- urine pregnancy test for female subjects of childbearing potential
- urine sample for UACR (2 consecutive day mid-stream, first-morning void urine samples to be collected at the subject's home on the morning before and the morning of Visit 7)
- complete blood count
- serum chemistry profile (including sUA and serum creatinine to calculate eGFR); see [Appendix A](#) for the evaluations to be performed
- thyroid hormones
- lipid panel

- urinalysis
- blood (plasma and serum) and urine sample for biomarkers (the mid-stream, first-morning void urine samples collected by the subjects at home will be used for the analysis of biomarkers)
- treatment-emergent adverse event recording
- concomitant medication review
- vital signs, consisting of supine blood pressure, supine pulse rate, and oral body temperature
- body weight

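### SAP 6.1 counts some protocol-compliant Visit 7 samples (Days 98–104) as Week 12, so the windowed Follow-up analysis loses them

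*SAP*

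**What the plan says.** The protocol sets both visits with a tolerance, the second relative to the first:

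- Protocol 7.5.4.5: "End of Treatment Visit 6: Study Day 84 ± 7 Days or Early Termination Visit".
- Protocol 7.5.4.6: "End of Study Follow-up (Visit 7): Visit 6/ET+28 ± 7 days".

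SAP 6.1 replaces these with fixed study-day ranges for UACR, serum chemistry and biomarkers:

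- "Week 12/ET (Day 84") takes Days 64–104.
- "Week 12/ET + 28 Days (Day 112") takes Day 105 and later.

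Where several visits fall in one range, "the measurement closest to the target day of the visit will be used in the analysis". For ties, "If the measurements are equally distant to the target day, then the later one will be used in the analysis". The ranges govern the by-visit analyses of the primary, secondary and other endpoints. Elsewhere, "All other analyses will use the nominal study visit as defined in the study schedule and eCRF".

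Follow-up is an analysed time point. SAP 3.2 lists change to the Follow-up visit in eGFR, UACR, renal biomarkers and sUA among the secondary endpoints. SAP 7.6.5.1 fits the LOCF version of the ANCOVA at Follow-up for eGFR, UACR and sUA, and leaves Follow-up data out of the MMRM. Biomarkers are described only (SAP 7.6.5.3).

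**The concern.** The Follow-up row is named relative to each subject's own end of treatment, but its range is a fixed study day. The two agree for a subject seen exactly on target. They need not agree for one who comes early within the protocol's tolerance. That subject's off-drug sample is then labelled as end of treatment.

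Follow-up is the one point that shows whether changes in UACR, eGFR and sUA reverse after treatment stops. The ANCOVA is the only inferential analysis of it. If an observed off-drug value is set aside and the gap is filled from Week 12, the Follow-up estimate is pulled towards the Week 12 estimate, and a reversal may be partly hidden.

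**Working it through.** **Inputs.** Visit 6: Day 84 ± 7. Visit 7: Visit 6 + 28 ± 7 days (both Protocol 7.5.4). Week 12 range Days 64–104, Follow-up range Day 105 onward, and the closest-to-target rule (SAP 6.1). On day numbering, "Day 1 is the first day of treatment", and dosing starts the day after Visit 3 (Day 0), so SAP days and protocol days coincide unless the first dose is late.

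**Plan's own figure.** 84 + 28 = 112, which matches the Follow-up target day.

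**Allowed days for Visit 7.** Earliest 77 + 21 = 98; latest 91 + 35 = 126. Days 98–104 are therefore valid Visit 7 days under the protocol and Week 12 days under the SAP.

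**Who is affected.** Visit 7 falls on or before Day 104 when Visit 6 day + gap ≤ 104. The gap is at least 21, so Visit 6 must be on or before Day 83. Affected gaps out of the 15 allowed (21–35 days):

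| Visit 6 day | 77 | 78 | 79 | 80 | 81 | 82 | 83 | 84–91 |
|---|---|---|---|---|---|---|---|---|
| Affected gaps | 7 | 6 | 5 | 4 | 3 | 2 | 1 | 0 |

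The total is 7 + 6 + 5 + 4 + 3 + 2 + 1 = 28 of 15 × 15 = 225 compliant pairs.

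**Which value is kept.** In all 28 pairs Visit 6 is 1–7 days from Day 84 and Visit 7 is 14–20 days from it. If Visit 6 has a value, it wins every time and Visit 7 is used in neither range. If Visit 6 has no value, Visit 7 is the candidate nearest the target and becomes the Week 12 value.

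**What fills the gap.** SAP 7.6.1 defines LOCF as carrying the last post-baseline value to a missing Week 12, and SAP 7.6.5.1 extends that model to Follow-up. On the windowed data, the last value before an empty Follow-up is Week 12, which here is Visit 6, at the end of treatment.

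**Share affected.** The documents do not give the distribution of actual visit days, so each row is an assumption. Visit 6 day and gap are taken as independent.

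| Assumed visit days | Share |
|---|---|
| Uniform over both allowed windows | 28/225 = 12.4% |
| Triangular around target | 5.1% |
| Truncated normal on target, SD 2 / 3 / 4 days | 0.4% / 3.1% / 6.1% |
| On average 3 days early at both steps, SD 3 | 28% |
| On average 5 days early at both steps, SD 3 | 58% |

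As a planning number, 132 × 0.9 ≈ 119 subjects. The uniform case gives 119 × 0.124 ≈ 15, or about 5 of 40 per group. SD 3 and SD 4 give 119 × 0.031 ≈ 4 and 119 × 0.061 ≈ 7. Actual Visit 7 attendance is not given.

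The count is sensitive to one day. If the windows are applied to the urine sample taken the morning before the visit, or if the first dose is a day late, the uniform count becomes 1 + 2 + … + 8 = 36, and 36/225 = 16%.

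**After the change.** Assigning Visit 7 by nominal visit leaves 0 of 225 pairs misclassified.

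**The case against.** The strongest reply is that little depends on this. A completer with a Visit 6 value keeps that value at Week 12, so the primary result and the MMRM do not change. Only one of four time points of secondary endpoints is touched, no decision rule rests on it, and the number of subjects may be very small if sites keep close to target days. All of this stands, and it limits the weight of the point.

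Four stronger readings are tempting, and the documents do not support them:

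- **That 12% is a ceiling.** It is the expected share under an assumed uniform, independent spread. Clustering makes it smaller and early visits make it larger.
- **That punctual completers lose data.** A subject seen on Day 84 has Visit 7 no earlier than 84 + 21 = Day 105, the first Follow-up day. Loss requires Visit 6 before Day 84 and the two steps together at least 8 days early.
- **That the values disappear.** All collected data are listed by visit (SAP 7.1), and the laboratory summaries in SAP 7.7.2 use nominal visits, so sUA and creatinine at Visit 7 still appear there. The loss is confined to the windowed analyses. It does mean that one sample can be Follow-up in a safety table and absent from the efficacy Follow-up.
- **That the rule removes the shortest washouts.** All affected gaps are 21–27 days, so there is a tilt, but the cut is by study day. Visit 6 on Day 77 with a 27-day gap (Day 104) is dropped; Visit 6 on Day 84 with a 21-day gap (Day 105) is kept.

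One could also argue that LOCF might draw on every recorded value, in which case the set-aside Visit 7 value would itself be carried to Follow-up. The SAP does not say this. Since 6.1 applies the windows to the by-visit analyses, carrying forward the windowed Week 12 value is the more natural reading.

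**Conclusion.** The SAP's fixed-day ranges contradict the protocol schedule on Days 98–104. For completers with Visit 6 on Days 77–83 and a Visit 7 on those days, the off-drug value leaves the windowed Follow-up analysis if Visit 6 has a value, and enters Week 12 if it does not. In the first case, as SAP 7.6.5.1 reads, the Follow-up ANCOVA would use an on-treatment value where an off-drug one was observed.

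That the conflict exists follows from the day arithmetic alone. Its size does not: it rests entirely on the assumed spread of visit days. For completers the primary endpoint is at risk only through a missing Visit 6 value. This is a modest defect in a secondary analysis, worth correcting because the correction is so cheap.

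**What to change.** In SAP 6.1, assign the Follow-up time point by nominal Visit 7 (28 days after Visit 6 or early termination) instead of Study Day 105 or later, and state that Visit 7 samples are not eligible for the Week 12 range. The SAP already uses nominal visits for its other analyses, so the cost is one sentence and a small programming change.

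Moving the boundary would also work for completers: a Follow-up range starting on any day from 92 to 98 misclassifies 0 of 225 compliant pairs. It would not work for subjects who stop early. For example, termination on Day 50 puts a visit 28 days later on Day 78, still inside Week 12. Nominal assignment covers both groups and is the better choice.
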